### **1.2.3 Background on Cobimetinib Monotherapy**

Cobimetinib is a reversible, potent, and highly selective inhibitor of MEK1 and MEK2, key downstream regulators of the MAPK pathway. MEK1 and MEK2 are responsible for activating ERK by phosphorylation. Cobimetinib inhibits ERK phosphorylation in xenograft tumor models to stimulate apoptosis and tumor regression. Cobimetinib has been studied alone or with other agents in more than 1000 adult cancer patients; the vast majority of patients had been treated with cobimetinib plus other agents, such as vemurafenib. The cobimetinib monotherapy trial is the first-in-human Phase I study MEK4592g, an open-label, safety, and pharmacokinetic (PK) dose-escalation study in patients with metastatic or unresectable solid tumors (Rosen et al. 2016). The recommended dose was 60 mg daily for 21 days followed by a 7-day break in dosing. As a single-agent, cobimetinib demonstrated anti-tumor activity in melanoma. In combination with other agents, cobimetinib has demonstrated anti-tumor activity in other tumor types, such as melanoma, lung, colon, and breast cancers (Larkin et al. 2014).

Cobimetinib (Cotellic®) is approved in the United States, European Union, Switzerland, and in multiple other countries across the world in combination with vemurafenib for the treatment of advanced *BRAF*-mutated melanoma.

Refer to the Cobimetinib Investigator's Brochure for cobimetinib for details on nonclinical and clinical studies.

### **1.2.4 Background on Atezolizumab Monotherapy**

Atezolizumab is a humanized IgG1 monoclonal antibody that targets PD-L1 and inhibits the interaction between PD-L1 and its receptors, PD-1 and B7-1 (also known as CD80),

both of which function as inhibitory receptors expressed on T cells. Therapeutic blockade of PD-L1 binding by atezolizumab has been shown to enhance the magnitude and quality of tumor-specific T-cell responses, resulting in improved anti-tumor activity (Fehrenbacher et al. 2016; Rosenberg et al. 2016). Atezolizumab has minimal binding to Fc receptors, thus eliminating detectable Fc-effector function and associated antibody-mediated clearance of activated effector T cells.

Atezolizumab shows anti-tumor activity in both nonclinical models and cancer patients and is being investigated as a potential therapy in a wide variety of malignancies. Atezolizumab is being studied as a single agent in the advanced cancer and adjuvant therapy settings, as well as in combination with chemotherapy, targeted therapy, and cancer immunotherapy.

Atezolizumab (Tecentriq®) is approved in the United States for the treatment of locally advanced or metastatic urothelial carcinoma and for the treatment of metastatic non–small cell lung cancer.

Refer to the Atezolizumab Investigator's Brochure for details on nonclinical and clinical studies.

### **1.2.5 Combined Inhibition of PD-L1 and MAPK Signaling Pathways as Potential Anti-Cancer Therapy**

Although checkpoint inhibitors have shown efficacy in a variety of tumors, only a proportion of the tumors are responsive, and most patients eventually progress and die from their disease. Moreover, there are still high unmet needs for patients with tumors for which checkpoint inhibitors are ineffective.

One potential mechanism to convert cancers that are otherwise resistant to immune checkpoint inhibitors is to recruit immune cells (ICs) to the tumor sites so that anti–PD-L1 can be effective in activating the local immune system against the cancer cells. Nonclinical models suggest that MEK inhibition may have pleiotropic effects that could impact the tumor immune microenvironment, as the MAPK pathway has been implicated in the immune resistance of tumors and inhibition of this pathway can lead to increase CD8-positive T-cell infiltration (Kakavand et al. 2015; Liu et al. 2015).

Within the tumor, MEK inhibition in tumors increases expression of the checkpoint receptor PD-L1, which could counteract the increased presentation of tumor antigens. MEK inhibition also results in increased major histocompatibility complex (MHC) class I expression and tumor antigen presentation, which acts to enhance tumor recognition by the immune system. Lastly, the MAPK pathway is known to regulate a number of cytokines and chemokines, such as VEGF, IL-6, IL-8, and granulocyte macrophage colony-stimulating factor, which may affect recruitment of vascular and other stromal cell types, including myeloid-derived suppressor cells (MDSCs), that can inhibit the anti-tumor activity of T cells (Bancroft et al. 2001, 2002; Sano et al. 2001; Phan et al. 2013).

Activity of MEK inhibition outside of the tumor cells may further contribute to the modulation of the immune microenvironment that could enable a more permissive immune reaction against the tumor. These effects include inhibition of tumor vascular maturity and integrity, tumor infiltration, activity of MDSCs, neutrophils, increased activity of antigen-presentation cells, such as macrophage and dendritic cells, and recruitment and activation status of T-cell subsets, including CD8-positive cytolytic and CD4-positive helper cells (Giordano et al. 2015; Liu et al. 2015; Loi et al. 2015).

Collectively, these effects enable tumors to demonstrate stronger anti-tumor responses with the combination of a MEK inhibitor and PD-L1/PD-1 blockade in multiple mouse models, including colorectal, breast, and melanoma models (Liu et al. 2015; Loi et al. 2015). Increased anti-tumor activity is associated with increased CD8-positive T-cell infiltration of tumors that express markers consistent with tumor-cell cytolytic activity. In a mouse model, the MEK inhibitor–rescued T cells appeared to be most effective in the presence of a PD-L1 blocking antibody; the MAPK axis is a key downstream pathway for the T-cell receptor (TCR) triggering. The TCR-driven death seemed to be working in parallel with the PD-1 axis (Ebert et al. 2016). The data suggest that MEK inhibition can modulate the tumor immune microenvironment and enable better tumor recognition and killing by the immune system, particularly when paired with a checkpoint inhibitor against the PD-1/PD-L1 axis.

### **1.2.5.1 Rationale for Combining Cobimetinib and Atezolizumab for Solid Tumors after Progression on Anti–PD-1/PD-L1 Therapy**

As detailed in Sections 1.1.1– 1.1.3, although anti–PD-1/PD-L1 therapies have benefited patients with certain solid tumors, response rates to anti–PD-1/PD-L1 therapies are low and patients eventually progress on treatment. Patients who do not respond or achieve disease stabilization are defined as having refractory disease or primary resistance, whereas patients whose tumors progress after initial response or stabilization are defined as having relapsed disease or secondary resistance. The molecular mechanisms of primary and secondary resistance to immunotherapy are poorly understood. However, the known effects of MAPK inhibitors, including cobimetinib, on the tumor microenvironment (see Section 1.2.5) include effects that may enable conversion to an immune-responsive phenotype, sensitize refractory tumors to anti–PD-1/PD-L1 agents, and/or re-sensitize relapsed tumors to these agents, leading researchers to the hypothesis that combining MEK inhibition with anti–PD-1/PD-L1 therapy may lead to improved efficacy.

### **1.2.6 Clinical Data: Cobimetinib in Combination with Atezolizumab**

#### **1.2.6.1 Phase Ib Study of Cobimetinib and Atezolizumab: Study GP28363**

Study GP28363 is a Phase Ib, open-label, multicenter, global study designed to assess cobimetinib and atezolizumab administered in combination to patients with metastatic or locally advanced (unresectable) solid tumors. The study has two stages: Stage 1 (dose escalation) and Stage 2 (indication-specific expansion cohorts and serial biopsy cohort).

In Stage 1, the recommended Phase II dose was established to be 60 mg of cobimetinib by mouth (PO) once a day (QD) for 21 consecutive days of 28 days (21 days on/7 days off [21/7] schedule) and 800 mg of atezolizumab by IV infusion every 2 weeks (Q2W). In the Stage 2 (expansion cohorts), cobimetinib plus atezolizumab is being studied in a variety of solid tumors, including *KRAS*-mutant and *KRAS* wild-type metastatic colorectal cancer (CRC) and *BRAF*V600 mutant and *BRAF*V600 wild-type metastatic melanoma.

### 1.2.6.2 Preliminary Results of Study GP28363

[REDACTED]

[REDACTED]

[REDACTED]

[REDACTED]

[REDACTED]

### Biomarker Data

Biomarker evaluation from the serial tumor biopsy cohort showed a 4-fold increase of CD8-positive T-cell infiltration in 75% of tumors as well as increases in PD-L1 and MHC-I expression (Bendell et al. 2016). The data support the hypothesis that

cobimetinib has beneficial immunomodulatory effects at the tumor site that allow for immune anti-tumor activity.

### Summary of Adverse Events

The safety-evaluable population consists of 150 patients who had received at least one dose of atezolizumab. All patients received cobimetinib. Overall, 96.7% of patients experienced at least one adverse event regardless of attribution; 65.3% experienced a Grade  $\geq 3$  adverse event; and 44.0% experienced a serious adverse event. There were five Grade 5 adverse events (3.3%) (see [Table 1](#)).

The most common adverse events (reported in  $\geq 20\%$  of patients) were diarrhea (69.3%), fatigue (52.7%), rash (46.0%), vomiting (38.7%), nausea (34.0%), pruritus (32.7%), decreased appetite (30.0%), constipation (28.0%), peripheral edema (26.0%), pyrexia (23.3%), acneiform dermatitis (23.3%), increased CPK (22.7%), dyspnea (20.0%), and anemia (20.0%). The most common Grade  $\geq 3$  adverse events ( $\geq 5\%$ ) were fatigue (9.3%), anemia (8.7%), and diarrhea (8.0%). Overall, 44% of patients experienced a serious adverse event.

**Table 2 Objectives and Corresponding Endpoints**

Objective(s)	Corresponding Endpoint(s)
Primary Efficacy Objective:	
• To evaluate the efficacy of cobimetinib plus atezolizumab by ORR	• Objective response, defined as a complete response or a partial response based on two consecutive tumor assessments $\geq 4$ weeks apart, as determined by the investigator according to RECIST v1.1
Secondary Efficacy Objective:	
• To evaluate the efficacy of cobimetinib plus atezolizumab	• OS, defined as the time from enrollment to death from any cause • PFS, defined as the time from enrollment to the first occurrence of disease progression, as determined by the investigator according to RECIST v1.1, or death from any cause (whichever occurs first) • DOR, defined as the time from the first occurrence of a documented objective response to disease progression, as determined by the investigator according to RECIST v1.1, or death from any cause (whichever occurs first) • DCR, defined as the proportion of patients with a complete response, a partial response, or stable disease at 16 weeks, as determined by the investigator according to RECIST v1.1

DCR=disease control rate; DOR=duration of response; ORR=objective response rate; OS=overall survival; PFS=progression-free survival; RECIST v1.1=Response Evaluation Criteria in Solid Tumors, Version 1.1.

**Table 2 Objectives and Corresponding Endpoints (cont.)**

Objective(s)	Corresponding Endpoint(s)
Exploratory Efficacy Objective:	

 
To evaluate the efficacy of cobimetinib plus atezolizumab with immune-modified RECIST
 
	
 
Objective response, defined as a complete response or partial response on two consecutive assessments <math>\geq 4</math> weeks apart, as determined by the investigator according to immune-modified RECIST
 
PFS, defined as the time from enrollment to the first occurrence of disease progression, as determined by the investigator according to immune-modified RECIST, or death from any cause (whichever occurs first)
 
DOR, defined as the time from the first occurrence of a documented objective response to disease progression, as determined by the investigator according to immune-modified RECIST, or death from any cause (whichever occurs first)
 
DCR, defined as the proportion of patients with a complete response, a partial response, or stable disease at 16 weeks, as determined by the investigator according to immune-modified RECIST
 

Safety Objective:	

 
To evaluate the safety of cobimetinib plus atezolizumab
 
	
 
Occurrence and severity of adverse events, with severity determined according to the NCI CTCAE v4.0
 
Change from baseline in targeted vital signs
 
Change from baseline in targeted clinical laboratory test results
 

Pharmacokinetic Objective:	

 
To characterize cobimetinib and atezolizumab pharmacokinetics
 
	
 
Plasma concentration of cobimetinib at specified timepoints
 
Serum concentration of atezolizumab at specified timepoints
 

Immunogenicity Objective:	

 
To evaluate the immune response to atezolizumab
 
	
 
Presence of ADAs during the study relative to the presence of ADAs at baseline
 

ADA=anti-drug antibody; DCR=disease control rate; DOR=duration of response; NCI CTCAE v4.0=National Cancer Institute Common Terminology Criteria for Adverse Events, Version 4.0; PFS=progression-free survival; RECIST=Response Evaluation Criteria in Solid Tumors.

**Table 2 Objectives and Corresponding Endpoints (cont.)**

Objective(s)	Corresponding Endpoint(s)
Exploratory Immunogenicity Objectives:	

 
To evaluate potential effects of ADAs
 
	
 
Relationship between ADA status and efficacy, safety, or PK endpoints
 

Biomarker Objectives:	

 
To explore biomarkers that are associated with the efficacy of cobimetinib plus atezolizumab
 
	
 
Genetic alterations, such as RAS mutations, as measured by next generation sequencing
 
Baseline immune contexture, such as TIL distribution, PD-L1 expression, and immune signatures, as measured by IHC and RNA sequencing
 

 
To explore mechanisms of acquired resistance to cobimetinib plus atezolizumab
 
	
 
Genetic alterations, as measured by next generation sequencing
 
Changes in immune contexture, such as TIL distribution, PD-L1 expression, and immune signatures, as measured by IHC and RNA sequencing
 

 
To assess the pharmacodynamic effects of cobimetinib plus atezolizumab treatment
 
	
 
TIL distribution, CD8, PD-L1, and stromal markers as determined by IHC
 
Immune-signatures, pathway activation signature, and stromal signature, as determined by RNA sequencing
 
Changes to circulating IC prevalence and distribution during treatment and at progression
 

ADA = anti-drug antibody; IC = immune cell; IHC = immunohistochemistry; OS = overall survival; PD-L1 = programmed death–ligand 1; PK = pharmacokinetic; TIL = tumor-infiltrating lymphocyte.

### **3. STUDY DESIGN**

#### **3.1 DESCRIPTION OF THE STUDY**

##### **3.1.1 Overview of Study Design**

This Phase II, open-label, multicenter, non-randomized, multi-cohort study is designed to evaluate the combination of cobimetinib plus atezolizumab in patients with advanced solid tumors. The study is designed with the flexibility to open new or expand existing cohorts if the initial efficacy outcome is promising and the safety outcome is acceptable. The Sponsor may elect to suspend a particular cohort at any time. The Sponsor may elect to not open or delay enrollment of a particular cohort.

There are seven patient cohorts in the study:

- Cohort 1: patients with SCCHN who are anti-PD-1 and anti-PD-L1 treatment naive
- Cohort 2: patients with UC who are anti-PD-1 and anti-PD-L1 treatment naive
- Cohort 3: patients with RCC who are anti-PD-1 and anti-PD-L1 treatment naive
- Cohort 4: patients with SCCHN whose disease has progressed while receiving anti-PD-1 or anti-PD-L1 therapy
- Cohort 5: patients with UC whose disease has progressed while receiving anti-PD-1 or anti-PD-L1 therapy
- Cohort 6: patients with RCC whose disease has progressed while receiving anti-PD-1 or anti-PD-L1 therapy
- Cohort 7: a biopsy cohort comprising patients with solid non-melanoma, non-hematologic tumors who previously developed primary or secondary resistance to an anti-PD-1 or anti-PD-L1 agent

[figure not shown]
The primary objective of the study is to evaluate the efficacy of cobimetinib plus atezolizumab in different solid tumor types as measured by overall response rate. The study will be conducted globally, and approximately 20 patients will be enrolled in each cohort with the opportunity to expand up to approximately 40 patients per cohort. Approximately 12 patients will be enrolled in Cohort 7.

The Sponsor will monitor the enrollment for each region (North America, Europe, and Pacific/Asia). To ensure balanced global enrollment, the Sponsor may institute temporary limitations on enrollment in certain regions in the event of disproportionate accrual of patients.

A schedule of activities is provided in [Appendix 1](#).

After signing informed consent, patients will undergo screening procedures that include laboratory tests (e.g., hematology, chemistries, liver function tests); left ventricular function evaluation (echocardiogram [ECHO] or multiple-gated acquisition [MUGA] scan); contrast-enhanced computed tomography (CT) or magnetic resonance imaging (MRI) scan of the chest, abdomen, and pelvis; and ophthalmologic assessments. Patients can be rescreened.

[figure not shown]
**Figure 1 Study Schema**

Primary endpoint: ORR  
 Secondary endpoints: OS, PFS, DOR, DCR

DCR = disease control rate; DOR = duration of response; ORR = objective response rate;  
 OS = overall survival; PFS = progression-free survival; RCC = renal cell carcinoma;  
 SCCHN = squamous cell carcinoma of the head and neck; UC=urothelial carcinoma.

[figure not shown]
**Figure 2 Study Dosing Schema: Cohorts 1–6**

D= day; PO=orally (by mouth).

**Figure 3 Study Dosing Schema: Biopsy Cohort 7**

A=atezolizumab; D=day; PO=orally (by mouth).

### 3.1.1.1 Cobimetinib and Atezolizumab Treatment Schedule

Cobimetinib will be administered orally at a starting dose of 60 mg QD starting on Day 1 through Day 21 followed by a 7-day rest of each 28-day cycle in all cohorts.

Atezolizumab will be administered by IV infusion at a fixed dose of 840 mg on Days 1 and 15 of each 28-day cycle. Patients in the biopsy cohort (Cohort 7) will begin dosing cobimetinib before atezolizumab and will receive 60 mg cobimetinib alone QD, starting on Day 1 through Day 14 for Cycle 1. Atezolizumab dosing (840 mg IV) will begin on Day 15 in Cycle 1 and will continue on Days 1 and 15 of every cycle thereafter. Both study drugs will be administered until unacceptable toxicity or loss of clinical benefit, as determined by the investigator, after an integrated assessment of radiographic and biochemical data, and clinical status (e.g., symptomatic deterioration such as pain secondary to disease). If one study drug is discontinued or temporarily withheld or dose reduced, the other study drug may be continued.

Because of the possibility of an initial increase in tumor burden caused by IC infiltration in the setting of a T-cell response (termed "pseudoprogression") with atezolizumab containing treatment, radiographic progression per RECIST v1.1 may not be indicative of true disease progression. In the absence of unacceptable toxicity, patients who meet criteria for disease progression per RECIST v1.1 while receiving cobimetinib and/or atezolizumab will be permitted to continue study treatment if they meet all of the following criteria:

- Evidence of clinical benefit, as determined by the investigator following a review of all available data
- Absence of symptoms and signs (including laboratory values, such as new or worsening hypercalcemia) indicating unequivocal progression of disease
- Absence of decline in Eastern Cooperative Oncology Group (ECOG) Performance Status that can be attributed to disease progression

- Absence of tumor progression at critical anatomical sites (e.g., leptomeningeal disease) that cannot be managed by protocol-allowed medical interventions
- Patient's written consent to acknowledge deferring other treatment options in favor of continuing study treatment at the time of initial disease progression

After discontinuation of study treatment, patients may receive any subsequent line of therapy as directed by their treating physician. Patients will continue to be followed after discontinuation of study treatment to monitor adverse events, response and duration of response, and survival (see Section 4.6.1).

### **3.1.1.2 Tumor Assessments**

Tumor response will be evaluated by either CT scan or MRI scan according to RECIST v1.1, as determined by the investigator (see Appendix 3). Any evaluable and measurable disease must be documented at screening and re-assessed at each subsequent tumor evaluation. Immune-modified RECIST will also be evaluated at the same time (see Appendix 4), as determined by the investigator. Investigators will assess tumor response at 8-week intervals, regardless of any dose delays or treatment cycles.

Patients who discontinue treatment for reasons other than disease progression (e.g., toxicity) will continue scheduled tumor assessments until disease progression, withdrawal of consent, study termination by Sponsor, or death, whichever occurs first.

In the absence of disease progression, tumor assessments should continue every 8 weeks regardless of whether patients start a new anti-cancer therapy, unless consent is withdrawn.

All patients will be followed for survival unless consent is withdrawn. In patients who are treated beyond progression, tumor assessments will be performed until discontinuation of treatment.

### **3.1.1.3 Tumor Biopsies**

#### **3.1.1.3.1 Non-Biopsy Cohorts (Cohorts 1–6)**

Baseline tumor tissue samples will be obtained from all patients, preferably by means of a biopsy performed at study entry. If a biopsy is not deemed feasible by the investigator, archival tumor tissue may be submitted after Medical Monitor approval has been obtained.

These samples will be utilized for biomarker research (see [REDACTED] and details on tissue sample collection in Section 4.5.5).

Patients will be asked to provide an optional biopsy during treatment on Day 15 of Cycle 1 ( $\pm 5$  days), provided the patient's disease is easily accessible and tumor biopsies can be performed with minimal risk and discomfort. The biopsy is for exploratory research on biomarkers associated with the MAP kinase pathway and immune-related

pathways, and for DNA and RNA extraction on non-inherited biomarkers (including, but not limited to, cancer-related genes).

Patients will undergo mandatory tumor biopsy sample collection, unless not clinically feasible, as assessed and documented by the investigator, at the time of first evidence of radiographic disease progression according to RECIST v1.1, within 14 days after radiographic progression, or prior to the start of new anti-cancer treatment, whichever is sooner. These samples will be analyzed to evaluate the utility of the biopsy in distinguishing pseudoprogression (caused by tumor-infiltrating ICs) from true progression. In addition, tumor tissue biomarkers related to resistance, disease progression, and clinical benefit of atezolizumab may be analyzed.

*For biopsies obtained during screening (fresh or archival) and during the conduct of the trial, histologic samples are required for patients with SCCHN or RCC. For patients with UC, cytological or histologic samples are acceptable.*

### **3.1.1.3.2 Biopsy Cohort (Cohort 7)**

Patients enrolled in Cohort 7, the biopsy cohort, must have at least two (preferably three) accessible lesions that meet the requirements specified in the eligibility criteria. Exceptions may be made if a patient has only one lesion that allows multiple biopsies following discussion with Medical Monitor. One pre-treatment, two on-treatment biopsies, and possibly one post-progression biopsy will be performed. If more than one biopsy will be obtained from one lesion, the lesion should be large enough to permit successive biopsies  $\geq 1$  cm apart. Investigators are strongly encouraged to obtain two on-treatment biopsies as described below. At a minimum, the biopsy obtained between Day 10 and 14 of Cycle 1 should be obtained to test for possible immunologic effects of cobimetinib alone.

Patients in the biopsy cohort will undergo biopsies according to the following schedule:

- A pre-dose biopsy will be taken before Day 1, Cycle 1 (not required if a fresh biopsy was provided during screening)
- On Day 1, Cycle 1, patients will start treatment with cobimetinib alone
- A mandatory on-treatment biopsy will be obtained between Days 10 and 14 of Cycle 1
- Patients will receive their first atezolizumab dose on Day 15 of Cycle 1
- A mandatory second on-treatment biopsy will be obtained during Cycle 2, 4–6 weeks after the first dose of atezolizumab to assess the combined effects of cobimetinib and atezolizumab
- An optional, post-treatment biopsy will be obtained at the time of radiographic progression

Patients in the tumor biopsy cohort whose tissue sample is not evaluable may receive study treatment but may be replaced for the purpose of serial biopsy assessment.

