### **3.3.2.1 Rationale for the Biopsy Cohort (Cohort 7)**

Cohort 7 is designed to allow assessment of the biological effects of cobimetinib on immune therapy. In this cohort, in Cycle 1 only, cobimetinib will be given for 14 days before initiation of atezolizumab treatment. Biopsies obtained before treatment start and between Days 10 and 14 of cobimetinib monotherapy period will allow elucidation of the effects of cobimetinib on tumor immune contexture. Additional biopsies taken during the combination treatment period and at radiographic progression will support evaluation of the effects of combination treatment on the tumor microenvironment and the identification of potential mechanisms of resistance to combination therapy.

During Cycle 2 and all subsequent cycles, patients in Cohort 7 will receive cobimetinib 60 mg QD 21/7 and atezolizumab 840 mg IV Q2W, the same dose and schedule as in Cohorts 1–6.

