## Appendix 1 Schedule of Activities (cont.)

ADA=anti-drug antibody; Discon=discontinuation; ECHO=echocardiogram; ECOG=Eastern Cooperative Oncology Group; eCRF=electronic Case Report Form; FU=follow-up; HBcAb=hepatitis B core antibody; HBsAg=hepatitis B surface antigen; HBV=hepatitis B virus; HCV=hepatitis C virus; IRR=infusion-related reactions; LVEF=left ventricular ejection fraction; MUGA=multiple-gated acquisition; PBMC=peripheral blood mononuclear cell; PK=pharmacokinetic; RECIST v1.1=Response Evaluation Criteria in Solid Tumors, Version 1.1; T3=triiodothyronine; T4=thyroxine; Tx=treatment; WGS=whole genome sequencing.

Notes: All assessments should be performed within  $\pm 3$  days of the scheduled visit, unless otherwise specified. On treatment days, all assessments should be performed prior to dosing, unless otherwise specified. On treatment days, pre-infusion laboratory samples should be drawn 0–4 hours before the start of infusion, and post-infusion laboratory samples should be drawn 0–30 minutes after the end of infusion, unless otherwise specified.

Assessments shaded in gray should be performed as scheduled, but the associated data do not need to be recorded on the eCRF (except in the case of an adverse event).

- a Results of standard-of-care tests or examinations performed prior to obtaining informed consent and within 28 days prior to Day 1 may be used; such tests do not need to be repeated for screening.
- b Patients who discontinue study drug will return to the clinic for a treatment discontinuation visit *within 30 (+ 3) days after the last dose*. The visit at which response assessment shows progressive disease may be used as the study discontinuation visit.
- c Visit not specified by the protocol. Assessments should be performed as clinically indicated.
- d Required follow-up information will be collected via telephone calls and/or clinic visits every 3 months until death, loss to follow-up, or study termination by the Sponsor.
- e Informed consent must be documented before any study-specific screening procedure is performed and may be obtained up to 28 days before initiation of study treatment.

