## Appendix 1 Schedule of Activities (cont.)

- 
- t Biopsy schedule for patients in Cohorts 1–6. Please see different biopsy schedule listed in the table for the biopsy cohort (Cohort 7). Fresh baseline tumor tissue collected during screening (or archival if fresh tumor biopsy cannot be performed); optional on-treatment biopsy at Cycle 1, Day 15 ( $\pm 5$  days); mandatory biopsy at progression if clinically feasible.
- u Mandatory pre-treatment biopsy
- v Biopsy Cohort 7, mandatory tumor biopsy done between Days 10 and 14 of Cycle 1.
- w Biopsy Cohort 7, second (mandatory) on-treatment biopsy will be done during Cycle 2, approximately 4–6 weeks after the first dose of atezolizumab.
- x Biopsy Cohort 7, optional post-treatment biopsy at the time of radiographic progression.
- y Biomarkers are collected until Cycle 3, Day 1 (including that visit) and then at treatment discontinuation.
- z Urine samples will be collected for urothelial carcinoma patients only: screening on Day 1 of Cycle 1; on Day 1 of Cycle 3; and at treatment discontinuation visit only.
- aa The initial dose of atezolizumab will be delivered over 60 ( $\pm 15$ ) minutes. If the first infusion is well tolerated, all subsequent infusions will be delivered over 30 ( $\pm 10$ ) minutes until loss of clinical benefit. Study drug administration may be  $\pm 7$  days.
- bb For patients in Cohorts 1–6 only.
- cc All patients will receive cobimetinib at a dose of 60 mg (three 20-mg tablets) orally once a day on Days 1–21 of each 28-day cycle. At least 7 days off cobimetinib are required prior to starting a new treatment cycle. Cobimetinib should be taken approximately the same time each day, and no later than 4 hours after the scheduled time.
-

## Appendix 2

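### The permitted window for Cohort 7's combination biopsy runs into the cobimetinib rest week: 7 of its 14 nominal days carry no scheduled cobimetinib dose

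*Combined protocol and SAP*

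**What the plan says.** Section 3.1.1.3.2 fixes the start of the clock for Cohort 7: "Patients will receive their first atezolizumab dose on Day 15 of Cycle 1". It then sets the second on-treatment biopsy: "A mandatory second on-treatment biopsy will be obtained during Cycle 2, 4–6 weeks after the first dose of atezolizumab to assess the combined effects" of both drugs. Appendix 1 marks this biopsy in the Cycle 2 Day 15 column, and footnote w to that mark repeats the window: "second (mandatory) on-treatment biopsy will be done during Cycle 2, approximately 4–6 weeks after the first dose of atezolizumab".

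The cobimetinib schedule is in Section 3.1.1.1: "Cobimetinib will be administered orally at a starting dose of 60 mg QD starting on Day 1 through Day 21 followed by a 7-day rest", in 28-day cycles and for all cohorts. Section 3.3.2.1 confirms it for this cohort: "During Cycle 2 and all subsequent cycles, patients in Cohort 7 will receive cobimetinib 60 mg QD 21/7". Appendix 1 footnote cc makes the break compulsory: "At least 7 days off cobimetinib are required prior to starting a new treatment cycle".

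The first on-treatment biopsy is due on Cycle 1 Days 10 to 14, during cobimetinib alone.

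**The concern.** The second biopsy exists to show what the two drugs do together, yet its window extends into days when only atezolizumab is being given. The first on-treatment biopsy is taken entirely on cobimetinib. If the second falls in the rest week, two things have changed between the samples: atezolizumab has been added and cobimetinib has been paused. For a marker that follows dosing closely, the difference between the two samples then has no single reading. With about 12 patients, there would be little scope to separate on-drug from off-drug samples afterwards.

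The window also stands apart from the other scheduled on-treatment biopsies. Cohort 7's first is on Days 10 to 14. The optional one in Cohorts 1 to 6 is on Cycle 1 Day 15 with a 5-day margin, that is Days 10 to 20. Both lie inside the 21 dosing days. The text available gives no reason for sampling in the rest week.

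**Working it through.** Inputs: first atezolizumab on Cycle 1 Day 15 and a biopsy window of 4 to 6 weeks within Cycle 2 (Section 3.1.1.3.2, Appendix 1 footnote w); cobimetinib on Days 1 to 21 and off on Days 22 to 28 of each 28-day cycle (Sections 3.1.1.1 and 3.3.2.1, footnote cc).

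Formula: study day = 28 × (cycle − 1) + cycle day.

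1. First atezolizumab: 28 × 0 + 15 = study day 15.
2. Window opens: 15 + 28 = 43, which is Cycle 2 Day 15 (43 − 28).
3. Window closes: 15 + 42 = 57, which is Cycle 3 Day 1 (57 − 56). The plan's window in weeks therefore fits its Cycle 2 limit except for this last day.
4. Limited to Cycle 2 (study days 29 to 56), the permitted days are 43 to 56: 56 − 43 + 1 = 14 days, or Cycle 2 Days 15 to 28.
5. With a cobimetinib dose: study days 43 to 49, 49 − 43 + 1 = 7 days.
6. Without: study days 50 to 56, 56 − 50 + 1 = 7 days. Share = 7/14 = 50%.

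How far the share moves under other readings:

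- Keeping Cycle 3 Day 1, a dosing day: 7/15 = 47%.
- Counting Day 22 as on drug, because it is about a day after the Day 21 dose: 6/14 = 43%.
- First atezolizumab 3 days early (study day 12), cobimetinib calendar unchanged: Cycle 2 Days 12 to 26, 5/15 = 33%.
- First atezolizumab 3 days late (study day 18), calendar unchanged: Cycle 2 Days 18 to 28, 7/11 = 64%.

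None of these readings removes the overlap. If the biopsy were held to Cycle 2 Days 15 to 21 (28 to 34 days after first atezolizumab), 0 of 7 days would be in the rest week.

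The Appendix 1 column does not settle the matter. The general note says: "All assessments should be performed within $\pm 3$ days of the scheduled visit, unless otherwise specified", and footnote w does specify otherwise. The same table row shows that the columns are nominal: the first Cohort 7 biopsy is marked under Cycle 1 Day 15, while its footnote sets Days 10 to 14. Read literally, Day 15 with a 3-day margin gives Cycle 2 Days 12 to 18, all on cobimetinib. But Day 12 is only 28 + 12 − 15 = 25 days (3.6 weeks) after first atezolizumab, short of the four weeks required.

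**The case against.** There are several fair points in favour of the plan.

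- **Timing in practice.** Patients already attend on Cycle 2 Day 15 for atezolizumab, and sites may do most biopsies around then. A reader might infer from the 50% that about 6 of 12 patients (12 × 0.5) would be sampled off cobimetinib. That needs biopsies spread evenly over the window, which no section states. The documents are compatible with anything from none to all. This point stands: the share describes calendar days only.
- **The rest week is part of the regimen.** Section 3.3.2.1 speaks of "Additional biopsies taken during the combination treatment period" and does not promise a dose on the day of sampling. A patient on full schedule at Day 22 has just finished 21 days of cobimetinib. The documents give no half-life and no rate at which the markers revert, so a reader who concludes that rest-week samples are uninterpretable goes too far. What survives is a concern for fast-moving markers; the pathway activation signature in Table 2 is a plausible candidate, though that is an assumption.
- **The cohort does not rest on this biopsy.** Section 3.1.1.3.2 names the Day 10 to 14 biopsy as the minimum, to test cobimetinib alone, and its comparison with the pre-treatment sample is untouched. It would be wrong to infer that the cohort loses its basis.
- **Other differences remain.** Even on Days 15 to 21 the two on-treatment samples differ in elapsed time, cumulative cobimetinib, an intervening rest week and possibly the lesion sampled. Moving the biopsy removes one source of variation, not all.
- **Unseen handling.** Section 6.8 is partly redacted and the laboratory manual is not included, so the absence of a rule for rest-week samples cannot be asserted.

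These points limit the consequence. They do not change the calendar, or the mismatch between the window and its stated purpose.

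**Conclusion.** The point holds as a minor one. On the nominal schedule, 7 of the 14 permitted days for the second on-treatment biopsy fall when no cobimetinib is scheduled. The share is 43% to 50% under other readings of the nominal window, and 33% to 64% if the first atezolizumab dose moves by 3 days with the cobimetinib calendar fixed. Off cobimetinib here means no scheduled dose; residual drug or tissue effect early in the rest week cannot be judged from the documents.

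The consequence is limited to patients actually biopsied in that week and to markers that respond quickly to dosing. The number of such patients cannot be predicted. Response rate, safety and the cobimetinib-alone comparison are not affected, and the study describes itself as hypothesis-generating only.

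**What to change.** In Section 3.1.1.3.2 and Appendix 1 footnote w, schedule the second on-treatment biopsy on Cycle 2 Days 15 to 21 while the patient is taking cobimetinib. Record the date of the last cobimetinib dose with each sample. Summarise separately any sample taken off cobimetinib, whether in the rest week or during an interruption. If rest-week sampling is intended, give the reason instead.

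The text should also say which limit governs when atezolizumab starts late: a 3-day delay leaves only Days 18 to 21 as dosing days at least four weeks on.

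This changes the sampling window only, with no change to dosing, procedures or patient numbers. The cost is a 7-day rather than a 14-day window for a mandatory invasive procedure, which may lose some samples, and the loss of the timepoints between five and six weeks.
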